
 Incidence, frequency, and duration of treatment emergent adverse events (TEAEs) and serious adverse events (SAEs) Change from Baseline in laboratory values Change from baseline in vital signs Mean Investigator-assessed LTS scores by visit (overall and sensitive areas) Tapinarof plasma PK parameters on Day 1, if data permit, including: 
 area under the plasma concentration versus time curve from time zero to the last quantifiable concentration (AUC_{0-last}) maximum plasma concentration (C_{max}) time to maximum plasma concentration (t_{max}) time of last quantifiable concentration (t_{last}) Tapinarof plasma concentration on Day 28 	
Secondary:	

 Change in vIGA-AD™ score from Baseline at each study visit Proportion of subjects who have a vIGA-AD™ score of clear or almost clear (0 or 1) at each study visit Proportion of subjects with \geq50% improvement in EASI score from Baseline at each study visit Proportion of subjects with \geq75% improvement in EASI score from Baseline at each study visit Proportion of subjects with \geq90% improvement in EASI score from Baseline at each study visit Mean change and percent change in EASI score from Baseline at each study visit Mean change and percent change in %BSA affected from Baseline at each study visit Mean change and percent change in BSA x vIGA-AD™ values from Baseline at each study visit Proportion of subjects with a Baseline PP-NRS score \geq 4 who achieve \geq 4-point reduction in the PP NRS from Baseline at each study visit Proportion of subjects \geq 12 years old with a Baseline PP-NRS score \geq 4 who achieve a \geq 4-point reduction in PP-NRS score from Baseline at each study visit Proportion of subjects 2 to $<$ 12 years old with a Baseline PP-NRS score \geq 4 who achieve a \geq 4-point reduction in PP-NRS score from Baseline at each study visit Mean change in PP-NRS score from Baseline to Day 28 at each study visit by age group 	
Statistical Methods:	
Safety Analyses:	

 Analyses of the safety endpoints will be based upon the Safety population, which is defined as all enrolled subjects who receive at least 1 application of study drug. 	

- AEs will be summarized as incidence rates of any AEs, TEAEs, AEs of special interest, treatment-related TEAEs, TEAEs leading to study drug discontinuation, TEAEs leading to study discontinuation, and SAEs.

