1.3.3 Overall Benefit Risk

Taking into account the measures taken to minimize risk to subjects in this study, the potential risks identified in association with tapinarof are justified by the anticipated benefits that may be afforded to subjects with AD.

2 Objectives and Endpoints

The objectives and associated endpoints of the study are as follows:

Objectives	Associated Endpoint
Primary	

To evaluate the safety and tolerability of tapinarof cream, 1% QD in pediatric subjects ages 2 to 17 years old with extensive ADTo evaluate the PK of tapinarof cream, 1% QD in pediatric subjects ages 2 to 17 years old with extensive AD	
Incidence, frequency and duration of TEAEs and serious adverse events (SAEs)Change from Baseline in laboratory valuesChange from Baseline in vital signsMean Investigator-assessed local tolerability scores (LTS) scores by visit (overall and sensitive areas)Tapinarof plasma PK parameters on Day 1, if data permit, including:
area under the plasma concentration versus time curve from time 0 to the last quantifiable concentration (AUC_{0-last})maximum plasma concentration (C_{max})time to maximum plasma concentration (t_{max})time of last quantifiable concentration (t_{last})Tapinarof plasma concentration on Day 28
Secondary	Secondary: 
To assess the efficacy of tapinarof cream, 1% QD in pediatric subjects ages 2 to 17 years old with extensive AD

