8.1.3 Adverse Events of Special Interest

In prior clinical studies, contact dermatitis, folliculitis, and headache have been identified as AEs of particular clinical importance and will be reported as AESIs in this study.

In each case study drug may be continued or discontinued, based on Investigator judgment, and may be restarted when the event resolves. In addition, the following information should be collected for each of these AESIs:

Contact Dermatitis

The study site should collect location, time to onset, duration, size, associated symptoms (itching, burning, pain), severity (mild, moderate, severe), concomitant medications used to treat, action taken with study drug and photograph the affected site (if possible). If the subject contacts the study site to report significant skin irritation at or near the site of study drug application between study visits, the subject should be brought in for an unscheduled visit, if possible.

Headache

The study site should collect time to onset, duration, severity (mild, moderate, severe), location (e.g., frontal, temporal, occipital, diffuse).

Follicular Event

The study site should collect the location, duration, size, associated signs and symptoms (itching, burning, pain erythema), severity (mild, moderate, severe), describe morphology [scale (keratotic/cornified) or no scale (non-keratotic/non-cornified)], time to onset, and photograph the affected site (if possible). Additional information regarding management of folliculitis is provided in Section 8.2.1.2.4.

In particular, the term ‘folliculitis’ may not correctly describe the morphology of the observed local follicular events as these appear to be more consistent with a keratoses pilaris-like follicular based papule. Tapinarof upregulates components of the stratum corneum, including involucrin, hornerin, and filaggrin and increased cornification at, and subsequent mechanical occlusion of, the follicular ostia has been suggested to be a potentially on target mechanism by which these lesions may develop in some individuals treated with tapinarof cream. Additional morphologic description will help to more fully and appropriately characterize these follicular events.

Possible descriptors include, but are not limited to:

- Folliculitis
 - Non-inflammatory

- Inflammatory
- Milia
 - Non-inflammatory
 - Inflammatory
- Keratosis pilaris
 - Non-inflammatory
 - Inflammatory

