Study drug application instructions will be reviewed at all post baseline clinic visits and during the planned study phone call. The time of the dose application and assessments will depend on the time of the clinic visit. Therefore, the timing of the clinic visit may lead to a change in the subject's chosen dosing time for that day.

On Day 28 of this study, a final PK sample will be collected, and subjects will have the option to enroll in a separate open-label long-term extension (OL-LTE) safety study for an additional 48 weeks. Subjects who choose not to participate in the OL-LTE safety study or who fail to qualify for participation in the OL-LTE safety study will complete a Follow-up Visit (Day 35) approximately 7 days after the end of treatment in this study. Subjects who withdraw from the study before Day 28 will complete an Early Termination Visit as their final visit and are not eligible for the OL-LTE safety study. Subjects that complete an Early Termination Visit will not complete a Follow-up visit.

Study duration for subjects who complete this study and who fail to qualify for participation in the OL-LTE safety study, or who qualify to participate in the OL-LTE safety study but elect not to enroll in that study is approximately 9 weeks in total. Study duration for subjects who complete this study and are eligible and decide to participate in the OL-LTE safety study is approximately 8 weeks in total.

Efficacy assessments will include validated Investigator Global Assessment for Atopic Dermatitis (v-IGA-ADTM) score, % body surface area (%BSA) affected, eczema area and severity index (EASI), and PP-NRS. Safety assessments will include AEs, clinical laboratory tests, physical examination, vital signs, and local tolerability scale (LTS) assessments.

Pharmacokinetics will be assessed at Days 1 and 28. The screening blood sample will be used for baseline PK if the subject is enrolled. Blood samples for PK should not be collected from any anatomic site where study drug has been applied in order to minimize potential contamination.

Refer to protocol Section 6 for descriptions of study procedures and assessments and protocol Section 7 for the Schedule of Assessments (Table 1) for timing of procedures and assessments.

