7. NOTATION OF TREATMENT GROUPS AND VISITS

Notation of treatment groups

The following notation of **treatment groups** will be used throughout the report:

Full Notation (as used in the study protocol)	Notation Used Throughout All Tables, Listings, and Figures
Tapinarof Cream 1%	Tapinarof Cream 1%

Visit terminology

Visit	Notation Used Throughout All Tables, Listings, and Figures
Screening, Days -30 through Day -1, Visit V1	Screening
Baseline, Day 1, Visit V2	Baseline
Week 1, Day 8, Visit V3	Week 1
Week 4, Day 28, Visit V4 (End of Treatment)	Week 4
Week 5, Day 35, Visit V5 (End of Study/Follow-up)	Week 5

Note: A phone call to assess AEs and concomitant medications, to review study drug application procedures, and to confirm subject's continued participation in the study will occur on Week 2 (Day 15).

Analysis visits

Study days are measured from date of first dose of study medication. Study days corresponding to measurements are calculated as:

- Assessment date – date of first dose + 1 if assessment date is on or after the date of first exposure of treatment.
- Assessment date – date of first dose if assessment date is before the date of first exposure of treatment.

All efficacy, PK, and safety endpoints will be analyzed according to the nominal visits (i.e., actual visit) except for assessments collected on early termination and unscheduled visits. Early termination and unscheduled visits will be re-numbered to an analysis visit based on their windowed visits defined by actual study day. If more than one visit occurs within a single visit window, then the analysis will take the one closest to the target day. If the 2 visits are equidistant from the target day, the visit with later date and time will be used.

The following analysis visit windows will apply to early termination and unscheduled visits:

Analysis Visit	Target Day	Analysis Visit Window
Baseline	1	1
Week 1	8	Post first dose to Day 18
Week 4 (End of Treatment)	28	Day 19 – Maximum (last day of treatment + 3 days, Day 31)

Analysis Visit	Target Day	Analysis Visit Window
Week 5 (End of Study)	35	>Maximum (last day of treatment + 3 days, Day 31)

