13.2 Adverse Events

All AE summaries will be restricted to treatment-emergent AEs (TEAEs), which are defined as those AEs that occurred after dosing and those pre-existing AEs (prior to first application of study drug) that worsened during the study. If it cannot be determined whether the AE is treatment-emergent due to a partial onset date, then it will be counted as such. The one exception will be the summary of Any AE which will include AEs not considered treatment-emergent. The summary of Any AEs will be reported in the Overall Summary of Adverse Events.

Verbatim terms in the eCRFs will be mapped to SOCs and PTs using MedDRA (Version 24.0).

For subjects not rolling over to the OL-LTE safety study, all reported AEs will be included in the open-label maximal use summaries. For subjects rolling over to the OL-LTE safety study, all

AEs with an onset date on or before the Week 4 visit date will be included in the open-label maximal use summaries.

Imputation of Start and End Dates of Adverse Event

To calculate duration of AEs, the following rules will be used where applicable to impute partial or completely missing start dates or end dates:

- If only the day is missing for a start date, the 1st of the month will be imputed. If the new estimated date falls before the date of first dose, while the known month and year match the month and year of the first dose, the date of first dose will be used as the new estimated date. The AE will be considered as a treatment-emergent AE (TEAE).
- If only the day is missing for an end date, the last day of the month will be imputed. If the new estimated date falls after the date of last study visit, the date of last study visit will be used as the new estimated date. Last study visit is defined as the Week 4 visit for those who elect to participate in the OL-LTE safety study, or the Week 5 Follow-up Visit for those who fail to qualify for participation in the OL-LTE safety study, or who qualify to participate but ultimately elect not to enroll.
- If both the day and the month are missing for a start date or end date, no imputation will be used, and the duration will not be calculated. However, if the year of start is the same or greater than the year of the first dose date, the AE will be considered as a TEAE.
- If the start date or end date is completely missing, duration will not be calculated. However, an event with completely missing start date will be considered as a TEAE.

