For treatment-emergent AESIs, summarization will be more extensive, reflecting the more detailed information collected. Information summarized will include number of events per subject, earliest onset day, duration (in days), causality, grade, and seriousness of AESIs, outcome, actions taken with study drug, assorted physical characteristics of the AESIs, and demographic/baseline characteristics and vIGA-AD™ status of the subjects experiencing them. Each type of AESI will be summarized separately. If a subject has more than one treatment-emergent occurrence of an AESI, the subject's maximum duration, highest levels of causality and seriousness, maximum grade and generally the most extreme level of each characteristic will be summarized. If an AESI was ongoing at end of study (EOS), it will not be included in the duration summary.

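### SAP 13.2 drops AESIs still ongoing at end of study from the duration summary, so the reported duration is expected to be too short unless late-onset events are systematically brief

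*SAP*

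**What the plan says.** SAP 13.2 summarises each AESI type (contact dermatitis, follicular events, headache) separately, with duration in days among the items. For a subject with several occurrences, the "maximum duration, highest levels of causality and seriousness, maximum grade and generally the most extreme level of each characteristic will be summarized". It then adds: "If an AESI was ongoing at end of study (EOS), it will not be included in the duration summary".

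Duration has standing in this study. The protocol synopsis lists "Incidence, frequency, and duration of treatment emergent adverse events (TEAEs") as a primary endpoint, and the table in Protocol Section 2 repeats it: "Incidence, frequency and duration of TEAEs and serious adverse events (SAEs"). The other TEAE summaries in SAP 13.2 are incidence rates, so the AESI summary is the only duration summary that the SAP specifies.

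Onset is collected for all three AESI types. For contact dermatitis, Protocol 8.1.3 says: "The study site should collect location, time to onset, duration, size, associated symptoms".

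The cut-off is not uniform:
- SAP 7 attaches the end-of-study label to one visit: "Week 5, Day 35, Visit V5 (End of Study/Follow-up".
- SAP 13.2, in its date-imputation rules, says: "Last study visit is defined as the Week 4 visit for those who elect to participate in the OL-LTE safety study". It uses Week 5 for subjects who do not roll over.
- SAP 4 says: "Subjects that complete an Early Termination Visit will not complete a Follow-up visit".
- Protocol 3.3 and 7.9 define end of study by the last subject, which is a study-level date.

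**The concern.** An AESI that is open at the last visit has lasted at least from its onset to that visit. Leaving it out keeps only the events short enough, or early enough, to finish inside a window of about four to five weeks. Taking the maximum per subject does not help. If a subject's ongoing episode is the longest, it is dropped and a shorter resolved one is reported, or the subject contributes nothing.

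Rollover subjects are observed for about 7 days less. The same course of AESIs would therefore give a shorter reported duration in a study where more subjects roll over.

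What is at stake is the descriptive duration of events that the protocol singles out as clinically important, in a component of a primary safety endpoint. AESI incidence, grade and outcome are not touched.

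**Working it through.** The plan gives no AESI duration, incidence or share ongoing, so there is no figure to reproduce. The check asks what the rule would report under stated assumptions.

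**From the documents.** Last visit is Day 28 (rollover) or Day 35 (others); the statistic is the median of the per-subject maximum; ongoing events are excluded.

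**Assumed.** Onset uniform over Days 1-28. Durations D exponential with mean m, independent of onset. Half of affected subjects last seen on Day 28 and half on Day 35. One, two or three occurrences in 60%, 30% and 10% of affected subjects. No end date recorded after the last visit.

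**Step 1, share of events ongoing.** Let C be the time from onset to last visit: uniform on 0-27 d (Day 28) or 7-34 d (Day 35). Then r = P(D > C) is
- Day 28: (m/27)(1 − e^(−27/m)) = 0.254 at m = 7 and 0.443 at m = 14;
- Day 35: (m/27)(e^(−7/m) − e^(−34/m)) = 0.093 and 0.269.

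**Step 2, true median.** Let G(p) = 0.6p + 0.3p² + 0.1p³ be the chance that all of a subject's occurrences meet a condition of probability p. G(p) = 0.5 at p = 0.6097, so the true median maximum is −m ln(1 − 0.6097) = 0.941m: 1.9, 6.6 and 13.2 d for m = 2, 7 and 14.

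**Step 3, subjects contributing no duration.** This is the average of G(r) over the two last visits: (0.173 + 0.059)/2 = 12% at m = 7 and (0.334 + 0.185)/2 = 26% at m = 14.

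**Step 4, reported median.** Let q(x) = P(D ≤ x and D ≤ C). For x up to 7 d, q = 1 − e^(−x/m) for Day 35; for Day 28, subtract [m − (x + m)e^(−x/m)]/27 from that. The reported median x solves [avg G(r + q) − avg G(r)] / [1 − avg G(r)] = 0.5.
- m = 7, x = 4.96: q = 0.467 and 0.508; G = 0.625 and 0.491, average 0.558; (0.558 − 0.116)/0.884 = 0.50.
- m = 14, x = 6.9: q = 0.344 and 0.389; G = 0.706 and 0.553, average 0.630; (0.630 − 0.259)/0.741 = 0.50.

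**Step 5, ongoing events kept at their duration to date.** Here P(min(D, C) ≤ x) = 1 − e^(−x/m) P(C > x). Averaging G over the two last visits gives 0.5 at x = 5.8 d (m = 7) and 9.6 d (m = 14).

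| Assumed mean | True median | SAP rule | Durations to date included |
|---|---|---|---|
| 7 d | 6.6 d | 5.0 d | 5.8 d |
| 14 d | 13.2 d | 6.9 d | 9.6 d |

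At a mean of 2 d the SAP rule gives 1.8 against 1.9 d. Simulation with 1,000,000 affected subjects per scenario agrees with these figures.

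**Sensitivity, by simulation.**
- If the sentence means that the whole subject is dropped when any occurrence is ongoing, the reported medians are almost the same (about 5 and 7 d), but 24% and 46% of affected subjects contribute nothing.
- If everyone is last seen on Day 28 rather than Day 35, the reported median is 4.4 against 5.5 d at m = 7, and 6.0 against 7.7 d at m = 14.
- Over 18 scenarios (exponential, lognormal or Weibull durations; onset Days 1-28 or 1-14; last visit Day 28, Day 35 or half each), the shortfall was 0-10% at a mean of 2 d, 0-33% at 7 d, 6-55% at 14 d and 24-67% at 21 d.
- Constant durations give no bias.
- In constructed cases where late-onset events were short, the direction reversed: a reported mean of 5.13 against 4.91 d, and a reported figure of 6.0 against 4.2 d, each with about 9% ongoing.

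**The case against.** The strongest case for leaving the rule alone has four parts.

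**The omission is visible.** SAP 6 shows the number of observations, SAP 13.2 summarises AESI outcome and lists every event, and Protocol 8.1 requires a narrative for each AESI. This stands: a reader who infers that ongoing AESIs are hidden goes further than the documents allow. But these displays do not correct the duration figure or label it as resolved events only.

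**Events may close later.** Protocol 8.3.2 follows AEs until resolution or stabilisation, and the study-level end-of-study date in Protocol 3.3 and 7.9 falls later than most subjects' last visit. If later end dates are recorded and used, fewer events are excluded and the sizes above are upper bounds in that respect. Protocol 8.3.1 limits this, because AE collection stops at the final visit, and the SAP does not say which end of study it means.

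**The direction is not guaranteed.** A reader might infer that any ongoing event, with varying durations, must make the summary too short. It need not: the reversed cases show that duration must also not depend strongly on onset day. The documents say nothing on that either way.

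**Kaplan-Meier is not a clean replacement.** Using one record per event, it estimates per-event duration (median 4.9 d at a mean of 7 d), not the per-subject maximum (6.6 d) that the SAP specifies. It is also imprecise: at an assumed 5-20% incidence, about 2-7 of 36 subjects are affected. With 7 affected subjects, its mean absolute error was 1.8 d against 1.6 d for the resolved-only median at a mean of 7 d, and 3.5 against 4.0 d at 14 d. This stands, and it is why the fix does not rest on it.

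**Conclusion.** The rule is wrong as written, and the point is minor. It discards right-censored events from the only duration summary that the SAP specifies, for a component of a primary safety endpoint. The reported duration is expected to be too short if some AESIs are ongoing, durations vary, and duration does not depend strongly on onset day. The bias is nil if no AESI is ongoing and small for brief events. In the main case the shortfall at a mean of 7 d is 1.6 d of 6.6 d, and at 14 d it is 6.3 d of 13.2 d. Both figures rest on the assumed durations, onset pattern and mix of last visits, since the documents supply none of these.

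A reader might infer that the primary safety assessment as a whole is compromised. The documents do not support that: the study is descriptive, with no formal hypothesis (Protocol 10.2), and no test or decision rule uses this figure.

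**What to change.** Replace the sentence in SAP 13.2 with:

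*An AESI with no recorded end date is treated as ongoing, and its duration to date is calculated to the subject's last study visit (Week 4 for rollover subjects, Week 5 for non-rollover subjects, the Early Termination visit for withdrawals, last contact for subjects lost to follow-up). A recorded end date, including one obtained in AE follow-up, is used as is. For each AESI type, the duration summary of resolved events is labelled 'resolved events only' and shown beside the number and percent of subjects with an ongoing event. The per-subject maximum is also shown with ongoing events included at their duration to date, labelled as a minimum.*

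In the imputation rules of the same section, add that the bar on calculating duration when the end date is completely missing does not apply to this display.

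The minimum label is needed because, as Step 5 shows, including durations to date moves the figure closer to the truth but leaves it short. A Kaplan-Meier median, one record per event and overall only, is optional and supportive. If used, state that it estimates per-event duration and is imprecise with few affected subjects.

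Cost: SAP wording, one extra count and one extra display line. No new data are needed, since onset is already collected.

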13.3 Local Tolerability Scale (LTS) Scores

Local tolerability scale scores will be summarized with frequency counts and percent by visit (through Week 4/End of Treatment [EOT]). Additionally, observed values and change from baseline will be summarized by treatment and visit.

Local tolerability scale scores and change from Baseline scores at the sensitive areas (face, neck, skin folds, axilla, inframammary, anal crux, and genitalia) where study drug is applied will be summarized descriptively by visit and area for Investigator overall assessment, as well as listed by subject and anatomical site.

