6.2.1 Assessments Completed by Investigator

6.2.1.1 Validated Investigator Global Assessment

The vIGA-AD™ of disease severity will be assessed at every clinic visit. The vIGA-AD™ is a global assessment of the current state of the disease. It is a 5-point morphological assessment of overall disease severity and will be determined according to the categories described in [Table 3](#) and [Appendix 3](#). To be eligible, subjects must have a vIGA-AD™ score of at least 3 or 4 at Screening and the Baseline visit (Day 1). Eli Lilly and Company (Lilly) developed the vIGA-AD™ scale for use in clinical trials. For more information on the vIGA-AD™ please refer to Appendix 3 and the website <http://www.eczemacouncil.org/research/investigator-global-assessment-scale/>

Table 3: Validated Investigator Global Assessment Scale for Atopic Dermatitis

Score	Category	Definition
0	Clear	No inflammatory signs of atopic dermatitis (no erythema, no induration/papulation, no lichenification, no oozing/crusting). Post-inflammatory hyperpigmentation and/or hypopigmentation may be present.
1	Almost clear	Barely perceptible erythema, barely perceptible induration/papulation, and/or minimal lichenification. No oozing or crusting.
2	Mild	Slight but definite erythema (pink), slight but definite induration/papulation, and/or slight but definite lichenification. No oozing or crusting.
3	Moderate	Clearly perceptible erythema (dull red), clearly perceptible induration/papulation, and/or clearly perceptible lichenification. Oozing and crusting may be present.
4	Severe	Marked erythema (deep or bright red), marked induration/papulation, and/or marked lichenification. Disease is widespread in extent. Oozing or crusting may be present.

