6.3.5 Investigator Assessed Local Tolerability Scale

At each specified study visit, the Investigator (or qualified evaluator) will assess the presence and overall degree of irritation at the application sites according to a 5-point LTS. The score will ideally represent an “average” across all application sites. To the fullest extent possible, the same Investigator (or designated evaluator) will perform all tolerability assessments for an individual subject throughout the study. If the subject is applying study drug to “sensitive areas”, a separate LTS will be used to assess the degree of irritation for each of these areas where study drug is being applied. The sensitive areas that will be assessed are face, neck, skin folds, axilla, inframammary, anal crux, and genitalia. An example of the LTS is shown in [Appendix 5](#). The LTS should be completed pre-dose at Baseline/Day 1, Day 8, and Day 28 when other

assessments are completed. Other than at the Baseline visit, the Investigator-assessed LTS should only be completed when the subject is currently receiving study drug (i.e. has applied at least one application in the last 48 hours).

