Appendix 5: Local Tolerability Scale Assessment

At each specified study visit, the Investigator (or qualified evaluator) will assess the presence and overall degree of irritation at the application sites, according to the 5-point scale below. The score will ideally represent an “average” across all application sites. To the fullest extent possible, the same Investigator (or designated evaluator) will perform all tolerability assessments for an individual subject throughout the study.

If the subject is applying study treatment to “sensitive areas” (e.g., genitals, face, neck, and skin folds), then also assess the degree of irritation for these areas.

Local Tolerability Scale – Dryness, Erythema, and Peeling

Score	Severity	Description
0	No irritation	No evidence of local irritation/intolerance
1	Mild	Minimal erythema and/or edema, slight glazed appearance
2	Moderate	Definite erythema and/or edema with peeling and/or cracking but does not require treatment modification
3	Severe	Erythema, edema glazing with fissures, few vesicles or papules
4	Very Severe	Strong reaction spreading beyond the treated area, bullous reaction, erosions

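### Local tolerability: improving AD can lower the mean LTS score and mask individual irritation, and no planned table counts the children who worsened

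*SAP*

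**What the plan says.** **Endpoint.** The protocol Synopsis lists "Mean Investigator-assessed LTS scores by visit (overall and sensitive areas") among the primary endpoints, next to TEAEs, laboratory values, vital signs and PK. Section 2 lists the same endpoint.

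**Scale.** Protocol Appendix 5 heads the LTS with "Dryness, Erythema, and Peeling". Grade 1 is "Minimal erythema and/or edema, slight glazed appearance", grade 2 is "Definite erythema and/or edema with peeling and/or cracking but does not require treatment modification", and grade 3 is "Erythema, edema glazing with fissures, few vesicles or papules". Protocol 6.3.5 asks for irritation at the application sites, ideally as an average over all of them, with separate scores for sensitive areas.

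**Timing.** "The LTS should be completed pre-dose at Baseline/Day 1, Day 8, and Day 28" (Protocol 6.3.5). Baseline is exempt from the rule that the child must currently be using the drug.

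**Analysis.** SAP 13.3 plans counts and percentages by visit, and then: "Additionally, observed values and change from baseline will be summarized by treatment and visit". Sensitive areas are summarised descriptively and listed by subject and site. Under SAP Section 6, continuous summaries give n, mean, SD, median, minimum and maximum, by age group and overall.

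**The concern.** The cream goes on AD lesions, so the skin rated for tolerability is largely diseased skin. A vIGA-AD score of 3, the minimum for entry, is described as "Clearly perceptible erythema (dull red), clearly perceptible induration/papulation" and/or lichenification. A rater who applies the LTS wording literally could give such skin a non-zero score before the first dose. That score cannot be drug irritation.

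If that happens, successful treatment of AD lowers the LTS. The mean and the mean change then move in the favourable direction for a reason unrelated to tolerability, and children who do become irritated are averaged away. The study has one arm, so no vehicle group shows what AD improvement alone does to the score. A reader of the study report could take a negative mean change as evidence of good tolerability in a pediatric maximal-use study.

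**Working it through.** The documents contain no LTS data and no power calculation to reproduce; Protocol 10.2 bases the sample size on feasibility. The check is therefore a comparison of wording, followed by arithmetic on assumed scores.

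**1. Overlap of signs** (Protocol Appendix 5, 6.2.1.1, 6.2.2)

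| LTS grade | Signs shared with vIGA-AD or EASI | Signs not shared |
|---|---|---|
| 1 | erythema, edema | glazed look |
| 2 | erythema, edema | peeling, cracking |
| 3 | erythema, edema, papules | glazing, fissures, vesicles |
| 4 | none named | spread beyond treated area, bullae, erosions |

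Grades 1 to 3 overlap with AD signs; grade 4 largely does not. Neither Protocol 6.3.5 nor Appendix 5 says whether AD signs count.

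**2. How far a mean can hide worsening.** Let a share q of children rise by u grades and the rest fall by an average of d grades as AD clears.

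Mean change = q·u − (1 − q)·d, which is zero at q = d/(u + d).

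Input from the documents: N = 36 in three cohorts of about 12. Assumed: u and d.

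Worked case, all 36 at grade 2 at Baseline, 7 rise to 3 and 29 fall to 1:
- Week 4 mean = (7×3 + 29×1)/36 = 50/36 = 1.39
- Mean change = 1.39 − 2.00 = −0.61, with 7/36 = 19.4% worse

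Largest number who can worsen while the mean change stays below zero:

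| Rise u | Average fall d in the others | Break-even q | Of 36 | Of 12 |
|---|---|---|---|---|
| 1 | 0.5 | 0.333 | 11 | 3 |
| 1 | 1.0 | 0.500 | 17 | 5 |
| 1 | 1.5 | 0.600 | 21 | 7 |
| 2 | 0.5 | 0.200 | 7 | 2 |
| 2 | 1.0 | 0.333 | 11 | 3 |
| 2 | 1.5 | 0.429 | 15 | 5 |

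**3. Do the other planned summaries give the count?** In the worked case the by-visit counts do show it, because nobody was at grade 3 at Baseline. With mixed baselines they need not. Take 12 children at each of grades 1, 2 and 3 at Baseline, and let k children go from 1 to 3 while k go from 3 to 1. For every k from 1 to 12:
- the counts stay 12/12/12
- the mean and median change are 0
- the minimum and maximum change are −2 and +2

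Only the SD moves. It is √(8k/35), which is 0.48 for k = 1, 1.17 for k = 6 and 1.66 for k = 12. It does not translate into a number of children. The maximum shows that someone worsened, not how many did.

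**4. The opposite assumption.** If every rater gives 0 at Baseline because no cream has been applied, no child can fall. The mean change is then zero or positive, and nothing is masked. If some raters give 0 and others score AD signs, change from Baseline mixes two different quantities.

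**5. Comparison within the SAP.** Laboratory data get shift tables (13.4). Markedly abnormal blood-pressure changes are tabulated separately (13.5). AESIs are summarised at each subject's most extreme level (13.2). The LTS gets none of these.

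**The case against.** Four points on the other side have weight.

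- **The scale asks for irritation, and score 0 means none.** Before the first dose a rater may reasonably give 0. A reader might infer from the overlap that the Baseline LTS measures AD and that masking must follow. The documents do not support this, because they neither require nor prevent scoring AD signs. The effect is possible, not established.
- **The mean is not the only output.** Counts by visit, the maximum change by age group, and subject listings (Protocol 10.1, SAP 6 and 13.3) leave worsening partly visible. A grade 4 score would show in the counts. With two post-baseline LTS visits and about 36 children, worst scores can be read from the listings by hand. This stands, but a primary endpoint should not depend on a hand count.
- **Local reactions have another route.** Contact dermatitis and follicular events are AESIs with detailed reporting (Protocol 8.1.3, SAP 13.2). A reader might take the LTS for the only primary measure of tolerability; it is one of several. This route is weaker for AD-like irritation, because Protocol 8.1.1 does not count expected signs of AD as AEs unless they are more severe than expected.
- **The overlap and its timing are partial.** Peeling, cracking, fissures and vesicles are not items of vIGA-AD or EASI. Treatment continues on improved skin, where irritation is easier to tell from AD. Protocol 1.2 dates the first efficacy responses in the earlier AD study to Week 2, so Day 8 should be less affected than Day 28.

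**Conclusion.** The concern holds in conditional form. LTS grades 1 to 3 overlap with AD signs, Baseline is scored before any drug on diseased skin, and no rule says whether AD signs count. If raters count them, a fall in mean LTS or a negative mean change can reflect AD response and can mask individual irritation, with no control arm to separate the two.

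The documents cannot size the effect. Under the assumed rises and falls above, the mean change can stay negative with between 7 and 21 of 36 children worse; if Baseline is scored 0, the masking is nil. The existing counts, extremes, listings and AESI reports are partial safeguards, but none states how many children worsened. No hypothesis test or success threshold depends on the mean, so what is at risk is interpretation. This is an inexpensive improvement to the analysis and not a flaw that invalidates the study.

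**What to change.** In SAP 13.3, for the overall score and each sensitive area, by age group and overall, add:

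1. a shift table of LTS grade from Baseline to each post-baseline visit;
2. the distribution of each subject's worst post-baseline score;
3. the number and percent of subjects with a rise of at least 1 grade from Baseline at any post-baseline visit.

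Show absolute post-baseline scores beside the shifts. A child scored 2 for AD at Baseline and 2 for new irritation later shows no shift, so shifts alone are not enough. State that in this single-arm study a fall in mean LTS may reflect AD response and is not by itself evidence of tolerability.

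Two further steps are tempting and are not advised: telling raters mid-study to score only cream-related irritation, and relabelling the Baseline score as disease signs. Together they would make each shift compare two different constructs. A new scoring rule could also split the data if scoring has begun; the protocol is dated June 2021 and the SAP September 2022.

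Cost: a few extra tables from data already collected. Limit: a shift still cannot fully separate an AD flare from irritation.
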